4.0 PATIENT SELECTION

4.1 Inclusion Criteria

- 4.1.1 Patients with AML who are refractory (up to salvage 2) or relapsed (up to 2nd relapse). For patients with prior MDS or chronic myelomonocytic leukemia (CMML) or MPN who transformed to AML, therapy received for MDS, CMML, or MPN is NOT considered as prior therapy for AML.
- 4.1.2 Prior therapy with hydroxyurea, chemotherapy, biological or targeted therapy (e.g.

FLT3 inhibitors, other kinase inhibitors), or hematopoietic growth factors is allowed.

- 4.1.3 Age ≥ 18 years
- 4.1.4 Eastern Cooperative Oncology Group (ECOG) Performance Status ≤ 2
- 4.1.5 Adequate organ function: total bilirubin ≤ 1.5 times upper limit of normal (x ULN) (≤ 3 x ULN if considered to be due to leukemic involvement or Gilbert's syndrome); aspartate aminotransferase or alanine aminotransferase ≤ 2.5 x ULN (≤ 5.0 x ULN if considered to be due to leukemic involvement)
- 4.1.6 Adequate renal function defined by an estimated creatinine clearance ≥ 30 mL/min according to the Cockcroft-Gault formula (or local institutional standard method)
- 4.1.7 Patients must provide written informed consent.
- 4.1.8 In the absence of rapidly progressing disease, the interval from prior treatment to time of initiation of 5-azacytidine and avelumab will be at least 14 days OR at least 5 half-lives for cytotoxic/noncytotoxic agents, whichever is longer. The toxicity from prior therapy should have resolved to Grade ≤ 1 , however alopecia and sensory neuropathy Grade ≤ 2 is acceptable. The half-life for the therapy in question will be based on published pharmacokinetic literature (abstracts, manuscripts, investigator brochure's, or drug-administration manuals) and will be documented in the protocol eligibility document. Since the effect of both avelumab and 5-azacytidine may be delayed, use of hydroxyurea for patients with rapidly proliferative disease is allowed before the start of study therapy and will not require a washout. Concurrent therapy for CNS prophylaxis or continuation of therapy for controlled CNS disease is permitted. Patients with CNS disease or leukemic brain metastasis must have been treated locally and be clinically stable for at least 2 weeks prior to enrollment and have no ongoing neurological symptoms that are related to the CNS disease (sequelae that are a consequence of the treatment of the CNS disease are acceptable).

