5.2 Schedule

The Investigator is responsible for completing the cohort summary template and submitting to the IND office Medical Monitor for review and approval prior to advancing subjects to the next protocol specified cohort/dose level. A copy of the cohort summary should be placed in the Investigator's Regulatory Binder under "sponsor correspondence". This should be submitted after the first six patients.

5.2.1 Patients will be treated according to the following schedule:

- 5-azacytidine will be administered subcutaneously (SQ) or intravenously (IV) for 7 days of every cycle with daily schedule of 7 consecutive days (Days 1-7) or for days 5-2-2 which is 5 consecutive weekdays (Days 1-5) with rest on the 2 weekend days (Days 6 and 7) and then dosing the first two weekdays of the next week (Days 8 and 9) of each 28-day cycle as determined by treating physician. Alternative dosing schedules such as 4-2-3 which is 4 consecutive weekdays (Days 1-4) with rest on the 2 weekend days (Days 5 and 6) and then dosing the first three weekdays of the next week (Days 7, 8, and 9) of each 28-day cycle or other schedules allowing the 2 day weekend interruption may be applied as long as we make every attempt to give the 7 days of azacytidine as consecutively as possible. This must be clearly documented in the medical record as determined by treating physician after approval from the PI. Both SQ

and IV forms of administration are FDA approved and considered interchangeable. Patients may start receiving 5-azacytidine by one route and changed to the other, and also administration schedules from one schedule and changed to the other at any time as needed based on patient and/or physician preference.

- Avelumab will be administered as an approximately 60 minute (+/- 30 minutes) IV infusion on Day 1 and day 14 (+/-3 days) of each 5-azacytidine cycle for the first 4 cycles or until CR (whichever occurs earlier) followed by a maintenance regimen (one dose of avelumab on day 1 of each cycle of 5-azacytidine). Patients who have evidence of budding relapse or seem to have clinical benefit may continue or revert back to receiving avelumab on Day 1 and day 14 (+/-3 days) of each cycle of 5-azacytidine. Patients may receive avelumab more or less frequently during the maintenance regimen only after discussion with the PI. Avelumab will be administered every cycle with no interruptions unless there are adverse events as described in Section 5.3.

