 - Grade 3 lymphopenia or leukopenia does not require dose delay.
 - However, patients with ALT or AST > 5 x ULN or total bilirubin greater > 3 x ULN or creatinine > 3 x ULN should have avelumab treatment interrupted.
- Any AE, laboratory abnormality, or intercurrent illness, which in the judgment of the investigator, warrants delaying the dose of study medication.
- Avelumab dose reductions are not permitted in this study (only dose delays when indicated).

Subjects may resume treatment with study drug when the drug-related AE(s) resolve to Grade ≤ 1 or baseline value, with the following exceptions:

- Subjects may resume treatment in the presence of Grade 2 fatigue
- Subjects who have not experienced a Grade 3 drug-related skin AE may resume treatment in the presence of Grade 2 skin toxicity
- Drug-related pulmonary toxicity, diarrhea, or colitis, must have resolved to baseline or at least \leq grade 1 before treatment is resumed
- Drug-related endocrinopathies adequately controlled may resume treatment

If the criteria to resume treatment are met, the subject should restart treatment at the next scheduled time point per protocol. However, if the treatment is delayed past the next scheduled time point per protocol, the next scheduled time point will be delayed until dosing resumes. Patients who receive combination therapy in whom continuation of 5-azacytidine is considered to be inadequate, or inappropriate (e.g., because of pancytopenia) can discontinue 5-azacytidine and continue with avelumab only.

If treatment is delayed > 8 weeks, the subject must be permanently discontinued from study therapy, except as specified in discontinuation section.

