5.3.4 Avelumab Discontinuation Criteria

The following ADRs require permanent treatment discontinuation of avelumab:

---**Any Grade 4 AEs require treatment discontinuation with avelumab** except for single laboratory values out of normal range that are unlikely related to study treatment as assessed by the Investigator, do not have any clinical correlate, and resolve within 7 days with adequate medical management

---**Any Grade 3 AEs require treatment discontinuation with avelumab except for any of the following:**

- Transient (≤ 6 hours) Grade 3 flu-like symptoms or fever, which is controlled with medical management
- Transient (≤ 24 hours) Grade 3 fatigue, local reactions, headache, nausea, emesis that resolves to Grade ≤ 1
- Single laboratory values out of normal range (excluding Grade ≥ 3 liver function test increase) that are unlikely related to study treatment according to the Investigator, do not have any clinical correlate, and resolve to Grade ≤ 1 within 7 days with adequate medical management
- Tumor flare phenomenon defined as local pain, irritation, or rash localized at sites of known or suspected tumor
- Change in ECOG PS to ≥ 3 that does not resolve to ≤ 2 within 14 days (infusions should not be given on the following cycle, if the ECOG PS is ≥ 3 on the day of study drug administration)

Any Grade 2 AEs should be managed as follows:

- If a Grade 2 AE resolves to Grade \leq 1 by the last day of the current cycle, treatment may continue.
- If a Grade 2 AE does not resolve to Grade \leq 1 by the last day of the current cycle, infusions should not be given on the following cycle. If at the end of the following cycle the event has not resolved to Grade 1, the subject should permanently discontinue treatment with avelumab AE (except for hormone insufficiencies, that can be managed by replacement therapy; for these hormone insufficiencies, up to 2 subsequent doses may be omitted).
- Upon the second occurrence of the same Grade 2 AE (except for hormone insufficiencies that can be managed by replacement therapy) in the same subject, treatment with avelumab has to be permanently discontinued.
- Infusion-related reactions, hypersensitivity reactions (Grades 1 to 4), and tumor lysis syndrome should be handled according to guidelines provided.
- Any dosing interruption lasting $>$ 8 weeks with the following exceptions:

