5.4 Duration of Therapy

In the absence of treatment delays due to adverse events, treatment may continue until one of the following criteria applies:

1. Clinically significant progressive disease, or
2. Intercurrent illness that prevents further administration of either treatment agent, or
3. Patient request, or
4. General or specific changes in the patient's condition render the patient unacceptable for further treatment in the judgment of the investigator, or
5. Unacceptable toxicity that in the opinion of the investigator makes it unsafe to continue therapy.

5.4.1 It is planned that up to a total of 24 cycles of therapy will be administered for patients deriving benefit from this regimen. Continuation of therapy for patients completing 24 cycles of therapy may be considered on a case- by-case basis after discussion with the principal investigator and IND Office.

5.4.2. A minimum of 1 full course (defined as the administration of 5- azacytidine for 7 days and one dose of avelumab) will be required for a patient to be considered as having received an adequate trial to evaluate efficacy. All patients receiving at least one dose of any of the two drugs will be considered evaluable for toxicity.

5.5 Supportive Care:

Supportive care measures including blood products, infection prophylaxis and growth factors will be administered according to institutional and MDACC Leukemia Department guidelines.

Management Algorithms for Treatment of Avelumab Related Adverse Events

Immuno-oncology (I-O) agents are associated with AEs that can differ in severity and duration than AEs caused by other therapeutic classes. Avelumab is considered an immuno-oncology agent in this protocol. Early recognition and management of AEs associated with immuno-oncology agents such as avelumab may mitigate severe toxicity. Avelumab has a known safety profile however, a general principle is that differential diagnoses should be diligently evaluated according to standard medical practice. Non- inflammatory etiologies should be considered and appropriately treated. Corticosteroids are a primary therapy for immuno-oncology drug-related adverse events, and avelumab is no exception. The oral equivalent of the recommended IV doses may be considered for ambulatory patients with low-grade toxicities. The lower bioavailability of oral corticosteroids should be taken into account when switching to the equivalent dose of oral corticosteroids.

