9.1.2 Investigator Discontinuation of Patient

The investigator may exercise medical judgment to discontinue study treatment if clinically significant changes in clinical status or laboratory values are noted.

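### Section 5.3.4 prints an unrecovered fall to ECOG 3 or worse as an exception to stopping avelumab, when its wording fits a reason to stop, and no other ECOG-based permanent stop exists

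*Combined protocol and SAP*

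**What the plan says.** Section 5.3.4 opens as a list of events that require avelumab to be stopped permanently. Its Grade 3 rule reads "Any Grade 3 AEs require treatment discontinuation with avelumab except for any of the following". Five bullets follow at one level, and the fifth is "Change in ECOG PS to ≥ 3 that does not resolve to ≤ 2 within 14 days". A parenthesis attached to that bullet adds that "infusions should not be given on the following cycle, if the ECOG PS is ≥ 3 on the day of study drug administration".

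The only other ECOG threshold in the protocol is the entry criterion in section 4.1.4: "Eastern Cooperative Oncology Group (ECOG) Performance Status ≤ 2".

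Section 5.2.1 schedules avelumab as an "IV infusion on Day 1 and day 14 (+/-3 days) of each 5-azacytidine cycle for the first 4 cycles", or until CR if that comes earlier. After that the regimen is one dose per cycle on Day 1, with some flexibility.

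**The concern.** A list of exceptions should name the events that are mild or brief enough to let treatment go on. A patient who falls to ECOG 3 or worse and is still there two weeks later is the opposite case. Under the printed text that patient falls within the exception, while one who recovers in time does not. Two clinicians could act in opposite ways: one following the list as printed, the other inferring that a stop was meant.

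This is an operative safety rule in a population that may enter at ECOG 2, one step from the threshold. What is at stake is a defined permanent stop for persistent functional decline. The sample size, stopping boundaries and planned analyses are unaffected.

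**Working it through.** The plan gives no figure to reproduce, so the check is mainly of the text.

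**1. Direction of each exception under the Grade 3 rule (section 5.3.4).**

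| Exception | Condition | Direction |
|---|---|---|
| Flu-like symptoms or fever | At most 6 hours, controlled | Passes |
| Fatigue, local reactions, headache, nausea, emesis | At most 24 hours, back to Grade 1 or lower | Resolves |
| Isolated laboratory value (Grade 3 or higher liver tests not included) | Back to Grade 1 or lower within 7 days | Resolves |
| Tumor flare | Localised; no time limit | Neutral |
| ECOG 3 or worse | Not back to 2 or better within 14 days | Fails to resolve |

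That is 3 transient or resolving + 1 local + 1 non-resolving = 5. The ECOG bullet alone makes non-recovery the condition.

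**2. Which reading is coherent.** As an exception, the bullet protects the patient who stays at ECOG 3 and not the one who recovers. As a stopping criterion under the section's opening sentence, it makes sense as written. As an exception with the verb reversed, it would also make sense. The printed combination is the one that does not.

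**3. Comparison within the same section.** A Grade 2 event still unresolved at the end of the following cycle requires permanent discontinuation. So does a second occurrence of the same Grade 2 event. Both rules exempt hormone insufficiencies that can be managed by replacement. As printed, an unrecovered fall to ECOG 3 has no corresponding permanent stop.

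**4. Search for another ECOG rule.** Thresholds appear in two places: section 4.1.4 (entry) and this bullet. Performance status is also named in section 7.1.1, Table 6 and the biomarker analysis paragraph of section 11, without a threshold. Sections 5.4, 9.1.2 and 9.1.3 contain no ECOG criterion.

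**5. What still constrains treatment.**

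- The parenthesis withholds infusions on the following cycle while ECOG is 3 or worse.
- An underlying Grade 3 or Grade 4 event requires discontinuation unless it is itself excepted (5.3.4).
- Clinically significant, drug-related non-skin events of Grade 2 or higher require avelumab to be delayed (5.3.3). Grade 2 fatigue and some laboratory abnormalities are excepted. The rule is not confined to the next cycle.
- A delay of more than 8 weeks leads to permanent discontinuation by default (5.3.3, 5.3.4). Exceptions cover prolonged steroid tapers, non-drug reasons approved by the PI, and patients deriving benefit after discussion with the PI. This limit is 56 days against 14, and 56 / 14 = 4 times as long.
- Clinically significant progression requires stopping (9.1.3).
- Judgment clauses apply. Section 5.3.3 allows delay for "Any AE, laboratory abnormality, or intercurrent illness, which in the judgment of the investigator, warrants delaying the dose of study medication". Section 5.4 ends treatment when changes in condition "render the patient unacceptable for further treatment in the judgment of the investigator". Section 9.1.2 says "The investigator may exercise medical judgment to discontinue study treatment if clinically significant changes in clinical status or laboratory values are noted".

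None of these is a permanent stop tied to ECOG, but together they leave few routes to continued dosing.

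**6. Reach of the parenthesis.** Cycles 1 to 4 hold 2 x 4 = 8 planned avelumab doses for a patient not yet in CR, of which up to 4 fall on Day 14. Day 14 is 14 - 1 = 13 days after Day 1. With the 3-day window it runs from Day 11 to Day 17, or 10 to 16 days after Day 1. That dose belongs to the same cycle, so wording about the following cycle does not expressly cover it when a decline is first seen after Day 1.

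**The case against.** The strongest reply is that bullet level in this section is poor evidence of meaning. Under the Grade 2 heading of section 5.3.4, two further bullets sit at the same level: one on infusion and hypersensitivity reactions of all grades, the other on interruptions of more than 8 weeks. Neither is a Grade 2 rule, and the second is plainly a stand-alone discontinuation criterion. The ECOG bullet may be another stand-alone item printed under the wrong sub-heading, or the list may have been flattened when the PDF was read.

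This stands as a caution. Nested bullets do survive in sections 5.3.3 and 5.3.4, and the ECOG bullet carries the same marker as the four exceptions with no lead-in of its own. A layout fault still cannot be excluded. If the bullet is misplaced in the source, that explains the error and supports moving it, but the printed rule is still wrong.

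A second reply is that ECOG is not an adverse-event grade, so the literal text exempts no underlying event that the Grade 3 or Grade 4 rules would otherwise stop. That also stands and limits the harm. It does not restore the ECOG stop that the bullet appears meant to supply.

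A third concerns Day 14. A reader might infer that Day 14 doses are unguarded. The documents do not support that, because the section 5.3.3 delay rule reaches them. A decline first seen after Day 1 has also lasted less than 14 days by nominal Day 14, so the 14-day criterion could not yet have been met. Only a minor clarification is left.

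**Conclusion.** The point holds as a drafting error in a safety rule. As printed, an unrecovered fall to ECOG 3 or worse is an exception to mandatory avelumab discontinuation, which reverses the evident intent, and the protocol has no other ECOG-based permanent stop.

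A reader might go further and infer that such patients may simply continue avelumab, or that only a one-cycle hold and investigator discretion protect them. The documents do not support either. The adverse-event stopping rules, the drug-related delay rule and the default stop after more than 8 weeks all remain, with their stated exceptions.

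The practical risk is therefore limited, and it cannot be put as a number because the documents give no expected count of affected patients. Confidence is medium: the conclusion assumes that the original document shows the same list structure. If the original shows the bullet as a separate stopping criterion, only the minor point about the parenthesis remains.

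**What to change.** First check the layout in the original document. Then move the ECOG bullet out of the exceptions list and state it as its own permanent-discontinuation criterion for avelumab: ECOG 3 or worse that has not returned to 2 or better within 14 days. If an exception was really meant, change *does not resolve* to *resolves*.

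As a minor clarification, say that the parenthesis applies to any avelumab infusion day, Day 1 or Day 14. Recording ECOG at the Day 14 avelumab visit would help in applying it. This is optional and adds no visit, since section 7.2.9 already has all avelumab given at the study centre's clinic.

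The cost is the wording of one bullet and its parenthesis. Sample size, stopping boundaries and analysis do not change.

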5.4 Duration of Therapy

In the absence of treatment delays due to adverse events, treatment may continue until one of the following criteria applies:

1. Clinically significant progressive disease, or
2. Intercurrent illness that prevents further administration of either treatment agent, or
3. Patient request, or
4. General or specific changes in the patient's condition render the patient unacceptable for further treatment in the judgment of the investigator, or
5. Unacceptable toxicity that in the opinion of the investigator makes it unsafe to continue therapy.

5.4.1 It is planned that up to a total of 24 cycles of therapy will be administered for patients deriving benefit from this regimen. Continuation of therapy for patients completing 24 cycles of therapy may be considered on a case- by-case basis after discussion with the principal investigator and IND Office.

5.4.2. A minimum of 1 full course (defined as the administration of 5- azacytidine for 7 days and one dose of avelumab) will be required for a patient to be considered as having received an adequate trial to evaluate efficacy. All patients receiving at least one dose of any of the two drugs will be considered evaluable for toxicity.

5.5 Supportive Care:

Supportive care measures including blood products, infection prophylaxis and growth factors will be administered according to institutional and MDACC Leukemia Department guidelines.

Management Algorithms for Treatment of Avelumab Related Adverse Events

Immuno-oncology (I-O) agents are associated with AEs that can differ in severity and duration than AEs caused by other therapeutic classes. Avelumab is considered an immuno-oncology agent in this protocol. Early recognition and management of AEs associated with immuno-oncology agents such as avelumab may mitigate severe toxicity. Avelumab has a known safety profile however, a general principle is that differential diagnoses should be diligently evaluated according to standard medical practice. Non- inflammatory etiologies should be considered and appropriately treated. Corticosteroids are a primary therapy for immuno-oncology drug-related adverse events, and avelumab is no exception. The oral equivalent of the recommended IV doses may be considered for ambulatory patients with low-grade toxicities. The lower bioavailability of oral corticosteroids should be taken into account when switching to the equivalent dose of oral corticosteroids.

Management Algorithms have been developed to assist investigators in assessing and managing the following groups of adverse events: Endocrinopathies, Gastrointestinal, Hepatic, Neurological Pulmonary, Renal and Skin. These algorithms are found in the “Avelumab Investigator Brochure” (Appendix C) and “Table 3. Management of immune related adverse events” of this protocol. The guidance provided in these algorithms should not replace the Investigator’s medical judgment but should complement it.

Finally, consultation with a medical or surgical specialist, especially prior to an invasive diagnostic or therapeutic procedure, is highly recommended.

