11.2 Statistical Design

Part a. Lead-in phase IB

The MTD is defined as the highest dose level with ≤ 1 out of 6 patients experience a DLT during the first 28 days of treatment. DLT is defined in section 5.2.2. The dosing schema for the combination treatment during the lead in phase is shown in Table 1 in section 5.2.1.

A Toxicity Summary will be submitted to the IND Office Medical Monitor, after the first three evaluable patients have completed their first cycle, and every three evaluable patients thereafter, prior to dose modification, expansion, or phase II initiation.

Part b. Phase II

An Efficacy/Toxicity Summary will be submitted every five evaluable patients during Phase II.

The historical experience in relapsed/refractory AML patient population is that historical responses (CR/CRp/CRi/PR/Hi/MLFS with >50% blast reduction) with single agent hypomethylator therapy (5-azacytidine or decitabine) or with hypomethylator combinations (azacytidine+revlimid, decitabine+myelotarg, azacytidine+vorinostat, decitabine+valproate) investigated at MDACC over the last 10 years are 10% ([name], Kantarjian H et al., European Hematology Association Conference, June 2016). The target ORR with the experimental treatment is 30%. This regimen of the combination treatment will be considered worthy of further investigation if it elicits an increase in ORR to 30% with acceptable toxicity. A >30% drug-related grade 3/4 toxicity rate is considered unacceptable. Thus, interim monitoring rules, assuming the prior distributions above, were constructed that meet the following two conditions,

- 1) Stop if $\text{Prob}\{p(\text{ORR}, E) < p(\text{ORR}, H) + 0.20 \mid \text{data}\} > 0.975$, or
- 2) Stop if $\text{Prob}\{p(\text{TOX}, E) > 0.30 \mid \text{data}\} > 0.975$,

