where $P(\text{ORR}, E)$ and $P(\text{TOX}, E)$ are the true ORR and toxicity rates for the combination treatment, and $p(\text{ORR}, H)$ is the true ORR rate of the standard treatment. The first rule provides for stopping the study if the data suggest that it is unlikely (i.e., probability < 2.5%) that ORR rate of the combination treatment is greater than the ORR rate of standard treatment by 20.0%. The second condition will stop the study early if excessive therapy-related grade 3/4 toxicity (>30%) is highly probable (i.e., probability >97.5%) for the combination treatment. Monitoring for toxicity and fertility will not begin until 5 patients have been evaluated, and cohort size for future evaluations is 5.

The monitoring rule for the toxicity rate, based on these assumptions and monitoring conditions above is found in Table 7. **For example, accrual will cease if 4 or more patients experience toxicities among the first 5 patients.**

Table 7. Stop accrual if the number of drug-related grade 3/4 toxicities is greater than or equal to indicated (i.e., # patients with toxicities) among the number of patients evaluated								
# patients evaluated	5	10	15	20	25	30	35	40
# patients with toxicities	4-5	7-10	9-15	11-20	13-25	15-30	17-35	Always stop

Monitoring the ORR rate, based on the above assumptions and monitoring conditions is found in Table 8. **For example, accrual will cease if no patients experience an overall response within 3 months of initiation of therapy in the first 10 patients treated.**

Table 8. Stop accrual if the number with overall response is less than or equal to indicated (i.e., # patients with overall response) among the number of patients evaluated							
# patients evaluated	5-10	15	20	25	30	35	40

# patients with overall response	0	0-1	0-2	0-3	0-4	0-5	Always stop
----------------------------------	---	-----	-----	-----	-----	-----	-------------

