All patients who received any dose of the study agent will be included in the analysis for efficacy and safety. Demographic/clinical characteristics (including duration of response) and safety data of the patients will be summarized using descriptive statistics such as mean, standard deviation, median and range. For the primary efficacy analysis, we will estimate the ORR for the combination treatment, along with the 95% credible interval. For the efficacy, a sample size of 40 patients ensures a posterior 95% credible interval for ORR of (0.17, 0.43), if the trial is not terminated early, under the assumption of a 30% ORR. Patients who drop out of the study before completing all the cycles will be treated as “failures” for the primary analysis. ORR during the study period will also be presented with the 95% confidence credible. The association between ORR and patient’s clinical characteristics will be examined by Wilcoxon’s rank sum test or Fisher’s exact test, as appropriate. Toxicity type, severity and attribution will be summarized for each patient using frequency tables.

The distribution of time-to-event endpoints (DFS and OS) including overall survival and progression free survival will be estimated using the method of Kaplan and Meier. Comparisons of time-to-event endpoints by important subgroups will be made using the log-rank tests. Paired t-tests will be used to determine the immunological and molecular changes in the peripheral blood and bone marrow from baseline to the time of response, and to the time of disease progression. Correlation analysis (such as logistic regression analysis) will be conducted to determine the relationship between induction of hypomethylation / DNA damage and clinical response.

A Toxicity Summary will be submitted to the IND Office Medical Monitor, after the first three patients have completed their first cycle of study therapy or administration is

discontinued, whichever comes first, and every three evaluable patients thereafter during the Lead-in Phase IB.

An Efficacy/Toxicity Summary will be submitted every five evaluable patients during **Phase II**.

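### Section 5.4.2 and the SAP give conflicting efficacy populations, and the denominator for the futility rule is left undefined

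*Combined protocol and SAP*

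**What the plan says.** Section 5.4.2, under Duration of Therapy, sets an efficacy minimum of one full course, made up of seven days of azacytidine and a single avelumab dose. That much "will be required for a patient to be considered as having received an adequate trial to evaluate efficacy". Its next sentence sets a lower threshold for safety: "All patients receiving at least one dose of any of the two drugs will be considered evaluable for toxicity".

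The Statistical Analysis Plan at the end of Section 11.2 sets a different efficacy population: "All patients who received any dose of the study agent will be included in the analysis for efficacy and safety". For the primary analysis it adds a failure rule, which begins: "Patients who drop out of the study before completing all the cycles will be treated as".

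For Phase II monitoring, Section 11.2 uses three terms for the unit:

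- Reporting in Phase II, in a sentence that begins: "An Efficacy/Toxicity Summary will be submitted every five evaluable patients during".
- The looks: monitoring "will not begin until 5 patients have been evaluated, and cohort size for future evaluations is 5". The column counts in Tables 7 and 8 are likewise of patients evaluated.
- The worked example for Table 8: "accrual will cease if no patients experience an overall response within 3 months of initiation of therapy in the first 10 patients treated".

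Section 11 does not define *evaluable*. Section 5.2.1.6 defines evaluability and replacement only for DLT in the lead-in. Section 11.1 defines ORR as response within 3 months of starting treatment.

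**The concern.** Two rules in current text point to different denominators for the primary endpoint, and neither is given precedence. Take a Phase II patient who stops after four azacytidine doses. Under the SAP this is a non-responder. Under 5.4.2 the patient has not had an adequate efficacy trial, yet is evaluable for toxicity.

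The choice is not neutral. Patients fail to finish a seven-day course mainly because of death, progression or toxicity, so leaving them out removes almost only non-responders. That raises the ORR and makes the futility rule less likely to stop an inactive regimen. The trial is single-arm and open-label, so no control arm would show the same distortion, and someone choosing the denominator after seeing data could cite either passage.

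**Working it through.** **Inputs (Section 11.2).** Response prior Beta(0.2, 1.8); comparison point 10% + 20% = 30%; stop for futility if P(ORR < 0.30 | data) > 0.975; looks at 5, 10, ..., 35 patients; Table 8 limits 0, 0, 1, 2, 3, 4, 5; 40 Phase II patients.

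**Step 1: reproduce the plan's figures.**

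- Interval: 12/40 responders gives Beta(0.2 + 12, 1.8 + 28), with 95% limits (0.165, 0.435). This matches the stated (0.17, 0.43).
- Table 8: stopping when Beta(0.2 + x, 1.8 + n − x) puts more than 0.975 below 0.30 reproduces every limit from n = 5 to 35. Table 7 reproduces in the same way with Beta(0.6, 1.4).
- Table 9: an exact binomial recursion over the looks, with response and toxicity independent, reproduces all 25 entries. Futility alone stops with probability 0.929 at ORR 10% and 0.512 at 20%; Table 9 at 10% toxicity has 0.9294 and 0.5119.

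The design arithmetic is sound. The open question is who is counted.

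**Step 2: apply 5.4.2 as a denominator rule.** Let a share e of treated patients stop before one full course, all non-responders. The ORR among the rest is p/(1 − e). The documents give no value for e; 5% to 25% is an assumed range. Looks stay at the same counts of remaining patients.

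| e | 30% ORR reads as | P(stop), true ORR 20% | P(stop), true ORR 10% |
|---|---|---|---|
| 0 | 30.0% | 0.512 | 0.929 |
| 5% | 31.6% | 0.467 | 0.915 |
| 10% | 33.3% | 0.421 | 0.897 |
| 15% | 35.3% | 0.373 | 0.875 |
| 20% | 37.5% | 0.325 | 0.848 |
| 25% | 40.0% | 0.278 | 0.815 |

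Example: 0.20/(1 − 0.20) = 0.25, and the recursion at 0.25 gives 0.325.

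These values assume that the look at 35 is reached. With e above 12.5%, 40 treated patients leave fewer than 35 (40 × 0.80 = 32). If early stoppers are not replaced, that look drops out and the stopping probability can only be lower still.

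**Step 3: single looks.** With 2 responders among 20 treated, the posterior probability of an ORR below 30% is 0.992, so accrual stops. If five early stoppers are removed, 2/15 gives 0.964 and accrual continues. Likewise 1/15 stops (0.994) and 1/10 continues (0.969).

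**Step 4: the final estimate, if 5.4.2 were applied there too.** 12/40 = 30.0% becomes 12/36 = 33.3%, interval (0.18, 0.48), with four patients dropped. With ten dropped, 9/40 = 22.5% becomes 9/30 = 30.0%, which is the target.

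**The case against.** A reader might infer that the plan excludes early stoppers from the primary ORR. It does not say so. Section 5.4.2 names no analysis set or table and sits among the treatment rules. The SAP is the specific text on the analysis population, and it keeps every dosed patient. This stands: the final ORR is inflated only if 5.4.2 is allowed to override the SAP.

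A reader might also infer that early stoppers count in Table 7 but not in Table 8. The two tables share the same column label and cohort size, and the Table 8 example speaks of patients treated. The split is a possible reading, not a stated rule. What remains is that three terms are used, none is defined for efficacy, and 5.4.2 holds the only efficacy threshold a reader can find. The any-dose sentence refers to the analysis and does not mention the interim looks.

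Finally, losses of 15% to 25% may be too high. On the Section 5.2.1 schedules the 5.4.2 minimum can be met by about day 7 to 9. If survival is assumed exponential, the 3.8 to 4 month figures in Section 2.1 imply about 4% to 5% dead by then. For a 4-month median at day 9, 1 − 0.5^(9/(4 × 30.44)) = 5.0%. Only the 1-month extreme gives 15% to 19%. Stopping for toxicity or progression adds to this, but the documents give no rate. So the lower rows of the table are the high end, and at 5% loss the effect is modest.

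**Conclusion.** The conflict is real and unresolved in current text, and it bears on the primary endpoint and on a stopping rule. Its main force is on futility monitoring. For the final ORR the SAP already gives a sound any-dose denominator, although its drop-out clause does not name early deaths.

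If 5.4.2 were applied, the error would run one way. At a true ORR of 20%, futility stopping falls by 0.045 with 5% loss (0.512 − 0.467) and by 0.234 with 25% loss (0.512 − 0.278). At a true ORR of 10% it falls by 0.014 (0.929 − 0.915) to 0.114 (0.929 − 0.815). These sizes rest on the assumed loss rates and on none of the early stoppers responding.

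The SAP's failure clause is itself loose. It covers anyone who leaves before completing all cycles, and Section 5.4.1 plans up to 24. Read literally, it recodes a patient who responded within 3 months and left later as a failure, which does not fit the 3-month endpoint. This is a should-fix reconciliation of wording.

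**What to change.** - In 5.4.2, limit the one-full-course minimum to a sensitivity analysis labelled as such.
- In 11.2, state that the denominator for Table 8 and for the primary ORR is every Phase II patient who received any dose of either drug, and use one term for that unit in the summary schedule, the tables and the worked example.
- State that a patient with no documented response within 3 months of starting treatment is a non-responder, including one who dies early or stops during course 1.
- Replace the failure clause about completing all cycles with this 3-month rule, so that a responder who leaves later is not recoded.

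The cost is a wording amendment. Tables 7 to 9 and the (0.17, 0.43) interval stand unchanged. The reported ORR may be slightly lower than one among course-1 completers, which can still be shown as the sensitivity analysis.
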